D1.3 Participant Exclusion Criteria.

For all participants: Any contraindication for MRI scanning is a general exclusion criterion irrespective of group. Primary intracerebral hematoma or subarachnoid hemorrhage, bi-hemispheric ischemic strokes, other concomitant neurological disorders affecting motor or cognitive function (e.g., dementia); moderate to severe global aphasia; visual impairment that precludes completion of scanner tasks; presence of any MRI risk factors such as an electrically, magnetically or mechanically activated metal or nonmetal implant including cardiac pacemaker, intracerebral vascular clips or any other electrically sensitive support system; pregnancy as the effect of MRI on the fetus is unknown; history of seizure disorder; claustrophobia; substance use disorder; psychotic disorders; moderate to severe traumatic brain injury

Stroke-group specific exclusion criteria are defined as: Primary intracerebral hematoma, or subarachnoid hemorrhage; bi-hemispheric or cerebellar strokes; other concomitant neurological disorders affecting upper extremity motor function; documented history of dementia before or after stroke; severe aphasia, particularly of receptive nature (NIHSS Language subsection ≥ 2 ²⁵) affecting their ability to understand the purpose of the study and give informed consent; uncontrolled hypertension despite treatment; intake of tricyclic anti-depressants or neuroleptic medication.

D1.4 Procedures

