Telephone Eligibility Screening (session 0). Potential participants of the stroke group will be pre-screened for eligibility regarding level of upper-extremity sensorimotor function and to exclude moderate or severe cognitive impairment. In lack of a validated phone proxy tool, we will use a questionnaire-based interview to estimate the level of sensorimotor function in a standardized and reproducible way (Appendix 1). Individuals reporting minimal voluntary whole-hand grip and release control will be invited for further assessment of in- and exclusion criteria if additionally identified as cognitively unimpaired, ambiguous, or mildly impaired by the Telephone Interview for Cognitive Status (TICS)^{26,27}. Eligibility for MR imaging is screened (MRI safety screen). Individuals who are able to complete these tasks demonstrate intact decision-making capacity. Individuals identified by the TICS as *moderately* or *severely impaired* will not be invited. The telephone screening will be done by a member of the administrative member of the research team who is trained to perform the questionnaire-based interview. To ensure to recruit only eligible participants for the patient group, telephone eligibility screening needs to be performed prior to obtaining informed consent. Data generated during this initial phone interview for participants not included in the study, will not be stored. Data of participants who are recruited and consented will be stored with the participant's data under the participant's study identification number after removal of identifiable information (name, contact details).

In-person Eligibility Screening (session 0). In cases in which in-person screening is feasible, e.g., if potential participants are already at the study site and have expressed interest in participating in this study, potential participants will be pre-screened based on the same information as in the telephone screening. One exception is the cognitive screening, which will be done with the Montreal Cognitive Assessment (MoCA)³⁶ instead of the Telephone Interview for Cognitive Status (TICS)^{26,27}. In these cases, no TICS data will be collected.

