Imaging Parameters (sessions 3 and 4). Scanning will take place at the Center for Biomedical Imaging on the Siemens 3T Prisma. Functional and structural scanning parameters are detailed in the **NI Core**. High-resolution structural, fluid-attenuated inversion recovery (FLAIR), diffusion-weighted (DWI), and arterial spin labeling (ASL) perfusion imaging will use in-house standard sequences and will be collected from all participants in session 3. The task-based fMRI sequence will be optimized for an event-related design with a TR of 2 seconds. For the resting-state data, a TR of 0.8 seconds will be used. Task-based and resting-state imaging will be collected in session 4 with varying protocols for participants of SG and CG as described in the timeline below and explicitly detailed in the information and consent form. All MRI sequences will be accompanied by electrical recording of physiological signals from the upper body (e.g., electrocardiogram, electrodermal analyses) to support processing of MRI data and for secondary analyses examining relationships between autonomic nervous system dysfunction, brain, and behavioral outcomes.

D2. TIMELINE

Participants of both groups (stroke, control) will undergo the same protocol, which includes 4 sessions (outlined in the table below).

Session Number	Task Description	Location at Medical University of South Carolina	Approximate Time Commitment
0	Telephone Eligibility Screening 
 • Sensorimotor function screening (Appendix 1) • Cognitive screening (TICS^{26,27}) • MRI Safety Screen 	Via telephone	30 minutes
1	Consent	Stroke Recovery Research Center or remotely through electronic consent	20-30 minutes
2	Multi-system Assessment 
All participants
 
 • Pregnancy Test • EHI[§] • Questionnaires (Appendix 2)[§] • Neuro-Cognitive and emotion Assessment 
Stroke group
 
 • physical Assessment of upper-extremity sensorimotor functioning • NIH-SS 	Stroke Recovery Research Center or partly remotely [§]	3 – 3.5 hours

	
 • SIS[§] 		

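### The uncontrolled-hypertension and tricyclic/neuroleptic exclusions bind the stroke group only, so the rules permit a group difference that the group-averaged RSA cannot adjust for

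*Combined protocol and SAP*

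**What the plan says.** **Exclusions.** D1.3 has one exclusion list for all participants and a second that opens "Stroke-group specific exclusion criteria are defined as". The second list ends with "uncontrolled hypertension despite treatment; intake of tricyclic anti-depressants or neuroleptic medication". The list for all participants mentions neither blood pressure nor these drugs. Its closing items are "history of seizure disorder; claustrophobia; substance use disorder; psychotic disorders; moderate to severe traumatic brain injury". It also excludes neurological disorders that affect cognition, with dementia as the example.

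**Cognitive pre-screen.** D1.4 (Telephone Eligibility Screening) says: "Potential participants of the stroke group will be pre-screened for eligibility regarding level of upper-extremity sensorimotor function and to exclude moderate or severe cognitive impairment". People whom the TICS classes as moderately or severely impaired are not invited. D2 says: "Participants of both groups (stroke, control) will undergo the same protocol". The session 0 row of its table lists the TICS without limiting it to one group.

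**Comparability and adjustment.** D1.1 asks for controls comparable in gender, age range and education. D3.3 names sex, age, race and ethnicity as covariates in follow-up analyses. Medication intake is recorded by questionnaire (D1.4, Appendix 2), which the D2 table places under all participants at session 2.

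**The concern.** Aim 1 describes learning-related connectivity in stroke survivors and in controls of comparable age and gender. The groups are not randomised, so the comparison depends on how each was selected. Nothing in the text ties the hypertension rule or the drug rule to having had a stroke. As written, a volunteer with uncontrolled hypertension, or one taking a tricyclic, is ineligible as a stroke participant but is not ruled out as a control by either exclusion list.

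If such controls are enrolled, and if the factor relates to the imaging signal or to learning, part of any difference between the groups would come from eligibility rather than from the lesion. According to the background section, altered dynamics in the stroke group are to supply brain-stimulation targets and support a follow-up proposal. The interpretation of the group difference therefore matters, even in a pilot.

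**Working it through.** The plan states no figure on this point, so there is none to reproduce. The check is a comparison of the text, with one illustration.

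**1. Where each factor is handled**

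| Factor | Stroke exclusion | Exclusion for all | Comparability target | Named covariate | Recorded for all |
|---|---|---|---|---|---|
| Uncontrolled hypertension | Yes (D1.3) | No | No | No | No measurement described |
| Tricyclic or neuroleptic intake | Yes (D1.3) | No | No | No | Yes, session 2 questionnaire |
| Dementia | Yes (D1.3) | Yes (D1.3) | No | No | Both groups assessed cognitively, session 2 |

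The first two rows have a gap for controls that no other section closes. The third does not.

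**2. Whether the analysis could correct for it.** In D3.2 the first-order matrices are averaged across participants within each group. The second-order correlations between regions are then computed on those averages. A control's characteristics are merged into the reference matrix before the network step, and no participant-level covariate enters there. With 15 controls, each contributes 1/15 = 6.7%. The univariate connectivity analysis mentioned in D3.4 could in principle take covariates, but these two factors are not among those named.

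**3. How likely the gap is to be used.** The documents give no prevalence of either factor among eligible controls, so p is assumed over a range. With independent recruitment of 15 controls, P(at least one) = 1 − (1 − p)^15 and the expected number is 15p.

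| Assumed p | Expected number | P(at least one) |
|---|---|---|
| 2% | 0.3 | 1 − 0.98^15 = 26% |
| 5% | 0.75 | 1 − 0.95^15 = 54% |
| 10% | 1.5 | 1 − 0.90^15 = 79% |
| 20% | 3.0 | 1 − 0.80^15 = 96% |

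This shows only that the gap could be used. It gives no bias, because the documents say nothing about how affected controls would differ on the imaging measures.

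**4. The cognitive pre-screen.** D1.4 words it for the stroke group and ties the telephone screen to recruiting eligible patients. D2 puts both groups through one protocol, and its table labels items by group at session 2 but not at session 0. That favours reading session 0 as common to both groups. On the other side, the D2 sentence counts 4 sessions while the table numbers them 0 to 4, so it is not certain that session 0 is included. Both groups also have a neuro-cognitive assessment at session 2 intended to confirm eligibility, but no cut-off is stated for it. The only explicit threshold is the TICS one, in the D1.4 paragraph worded for the stroke group.

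**The case against.** The strongest reply is that controls are already filtered. They are called healthy volunteers, and neurologically healthy in E1. Psychotic and substance use disorders are excluded in both groups, which may remove some neuroleptic users. This stands in part: it reduces the gap by an unknown amount. It does not close it, because healthy is not defined for blood pressure or medication and those exclusions do not address tricyclics or hypertension.

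A second reply is that either rule may have a stroke-specific safety reason. The documents give none, so this cannot be excluded. It is why the hypertension rule may be justified instead of extended.

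A third is that this is a pilot for feasibility and effect sizes, that D3.1 rests on within-group effects, and that several contrasts (sequence against random cues, one hand against the other) lie within participants. That stands. The consequence is limited to interpreting the difference between groups and does not reach every result.

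A reader might also infer that a control could fail the cognitive screen and still be enrolled. The documents do not establish this. D2 lists the TICS at session 0 without a group limit, the phone-screen text in E2 is not limited to patients, dementia is excluded for all, and both groups are assessed cognitively at session 2. What remains is an inconsistency between D1.4 and D2.

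**Conclusion.** The point holds as a gap in the eligibility rules. Two exclusions apply to one group only, without a stated reason, and neither comparability targets nor named covariates compensate. The group-averaged RSA cannot adjust for the factors afterwards. The rules permit a selection difference but do not demonstrate one.

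Its size and direction are unknown. The 26% to 96% range rests wholly on the assumed prevalence of 2% to 20% and on independent recruitment. Two stronger readings should be resisted:

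- That the gap would hide a stroke deficit. This requires affected controls to perform worse, which the documents do not show.
- That a hypothetical shift in the control mean can be judged against the 0.33 to 0.52 in D3.1. Those are within-group effect sizes for change from before to after learning, not differences between groups, and any assumed shift would itself have no source in the documents.

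On cognition, the conclusion is only that D1.4 and D2 must be reconciled.

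**What to change.** 1. Move the tricyclic/neuroleptic exclusion in D1.3 to the list for all participants. Apply it with the medication questionnaire that everyone already completes, and check the answers before scanning.
2. Do the same for uncontrolled hypertension, by self-report or history, or state why the rule is specific to stroke.
3. Report both factors by group.
4. Reconcile D1.4 with D2 so that it is clear that the same cognitive threshold applies to controls. Because in-person screening replaces the TICS with the MoCA and gives no cut-off, state how that route applies the threshold too.

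The cost is modest but goes beyond wording. A few more control volunteers would be screened out. The medication questionnaire now comes at session 2, after consent, so asking at session 0 would avoid consenting people who are then excluded. No blood-pressure measurement is described anywhere, so a history question would have to be added. The change must come before controls are scanned, because design can no longer correct the selection after that.

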We still do not know enough about how a focal lesion impacts the dynamics within brain circuits that govern motor learning and how this relates to maladaptive plastic changes. Filling this knowledge gap builds the basis for designing interventions that causally target experience-dependent maladaptive changes which negatively impact the patient's recovery (e.g., leading to disuse of the paretic hand). With this JI project, we will generate pilot data serving as the first evidence for motor learning-related network dynamics in the chronic phase after stroke (aim 1) and their link with biomarkers of recovery of upper-extremity sensorimotor function (aim 2).

AIM 1 To characterize motor learning (ML)-related neural network dynamics in the presence of a focal lesion, we will use a representational statistical modeling approach¹⁸ to describe learning-related connectivity changes based on task-based functional magnetic resonance imaging (fMRI) in stroke survivors (≥ 6 months post-lesion, stroke group SG) and healthy volunteers of comparable age and gender (control group, CG). Functional connectivity patterns will be modeled throughout the acquisition phase to capture the temporal trajectory of encoding-related network changes.

AIM 2 To understand the association between ML-related network dynamics and biomarkers of recovery, we will comprehensively describe upper-extremity sensorimotor functioning and impairment for the individuals in the SG and statistically integrate these biomarkers of recovery with the ML-related network dynamics within a separate representational model.

B. BACKGROUND AND SIGNIFICANCE

Recovery of upper extremity function remains dissatisfying for the majority of stroke survivors with sensorimotor impairment¹⁹, which represents a major hindrance to independence in daily life²⁰. Within the field of rehabilitation research, learning mechanisms have long been a major area of interest because they are considered one key player in functional recovery. This basic premise goes back to seminal work that established the brain's capacity to change in response to environmental stimuli and learning, i.e., experience-dependent plasticity^{21,22}.

However, it is evident that plasticity does not have purely beneficial effects on recovery³ but that also negative consequences such as learned disuse of the paretic hand can be observed¹.

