Recruitment. This study will recruit from the Registry for Stroke Recovery (RESTORE-Pro#00037803, IRB approved 9/6/14) which is a research tool sponsored by the National Institutes of Health (NIH) Center of Biomedical Research Excellence (COBRE) in Stroke Recovery with participants consented for future contact to support stroke recovery research conducted at MUSC. Trained RESTORE staff will query the registry for potential volunteers and provide the Principal Investigator (PI) or a member of the research team with the contact information of subjects who meet their criteria. Since these patients have already consented to being contacted for future research, the PI or a member of the research team will contact potential volunteers to further screen for potential enrollment. Contact will be sought via the preferred option indicated by the patient in the registry, e.g., via phone or email.

Recruitment of patients is feasible as it will happen in collaboration with the QBAR Core therapist team and capitalizing on the RESTORE database with over 800 participants, potentially eligible for this study. Volunteers for the control group will feasibly be recruited through the same channel and from spouses of patients and word-of-mouth to assure comparability concerning age, gender, and confounding variables such as education level. In addition, the potentially interested people will be accessed through flyers distributed digitally through MUSC information screens, the online platform Yammer.com, as well as through the MUSC Wellness Center.

Participants. For the initial pilot phase and the main study, chronic stroke survivors (time since stroke greater than or equal to 6 months) will be recruited. Acute stroke survivors (time since stroke less than 6 months) are excluded to minimize confounding from the spontaneous recovery of cognitive functioning.

D1.2 Participant Inclusion Criteria.

For all participants: Adult volunteers (age ≥ 18 years) with right-hand dominance²³ will be recruited for the stroke and control group.

Stroke-specific inclusion criteria are defined as (1) ischemic or hemorrhagic lesion with (2) subcortical or cortical tissue involvement, and (3) in the chronic phase (>6 months) after their index lesion, (4) voluntary whole-hand grip force (MRC, Medical Research Council scale for muscle force ≥ 2 ²⁴) and repeated release (standardized as a reduction of 50% of maximum voluntary contraction measured with a dynamometer).

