Informed Consent (session 1). Informed consent can be obtained in a written fashion by one of the members of the study team. Participants will be provided with ample time to review the consent document prior to discussion with a member of the study team. The nature of the study will be explained by a member of the study team in lay terms. If the participant or control agrees to participate in the study, they will sign and date the informed consent and HIPAA forms (or combined consent/HIPAA if applicable). They will also be informed that they may choose to withdraw from the study at any time. Participants will be informed that their decision regarding participation will not affect their clinical care in any way. A copy of the signed informed consent and HIPAA will be provided to participants.

Alternatively, electronic consent (eConsent) will be obtained through the REDCap system. A member of the research team will reach out to the participant by phone to provide details of the study. If the participant agrees to participate, a link to the REDCap eConsent will be provided to the participant via a hyperlink (text or email), and a member of the study team will review the consent document over the phone or via videoconferencing with the participant. The participant will electronically sign the eConsent and submit the REDCap survey. The study team member will then electronically sign the eConsent and print a PDF of the document. The signed PDF will be emailed or mailed to participants for their records. eConsent will be implemented at sites that support this method of consent.

Multi-System Assessment (session 2). Following consent, participants of both groups will be assessed regarding their neuro-cognitive and emotional functioning to further assure eligibility. Handedness (for participants of the stroke group this relates to pre-morbid status) will be assessed with the Edinburgh Handedness Inventory²³.

In addition, participants of the stroke group undergo the assessment of their upper-extremity sensorimotor functioning as well as the evaluation of stroke-related quality of life (SIS-3.0^{20,28}). General severity of stroke-related symptoms will be quantified with the NIH Stroke Scale (NIH-SS)^{29,30}. The NIH-SS will be performed by the PI or research staff certified for testing the NIH-SS.

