Sleep and vigilance screening. General sleep quality is quantified with the Pittsburgh Sleep Quality Index (PSQI)⁴³ once in session 2. Sleep duration and quality of the night preceding each individual experimental session are assessed with the respective items of the St. Mary's sleep questionnaire⁴⁴. Before the task training and retest sessions, self-perceived vigilance is evaluated with the Stanford Sleepiness Scale (SSS)⁴⁵ and additionally quantified objectively with the psychomotor-vigilance task (PVT)⁴⁶. Except PSQI, all of the above-mentioned sleep and vigilance screening assessments are performed on both experimental sessions (session 3 and 4). All sleep and vigilance screening will be performed by the PI or a member of the research team.

Additional Questionnaires will be used to collect information about the participant's demographics including age, gender, level of education in addition to medication intake (Appendix 2).

To reduce the burden for those participants who have participated in a study at the Stroke Recovery Research Center involving the same standardized assessments and questionnaires and consented to data sharing, we will use the already available data if these have been collected within ≤30 days.

Two-layered Learning Task (sessions 3 and 4). We will adapt an established sequence learning paradigm^{47,48} for the use in patients with sensorimotor impairment of the upper extremity. Two layers of implicit sequential information (Figure 1) are implemented in the experimental paradigm through visual stimuli on a computer screen to distinguish the two modes of implicit learning. Behavior is captured with whole-hand grip-force transducers (the hand-held interface) requiring minimal active range of motion and voluntary muscle force.

[figure not shown]

Figure 1 Behavioral paradigm and participant flow. A) Experimental set-up showing visual stimuli with imperative cue (green) and force feedback (yellow) to implement the stimulus-response mapping of cue positions and input force level scaled relative to individual

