3	
MRI scanning and task familiarization
 
 • MRI Safety Screen • Sleep and vigilance screening 
MRI sequences:
 
 • FLAIR • DWI • ASL • T2* weighted sequence (resting-state) • Physiological recordings 
Learning task:
 
 • Task familiarization (in the mock scanner) 	Center for Biomedical Imaging	2 – 2.5 hours
4	
MRI scanning during task practice
 
MRI Safety Screen
 
Sleep and vigilance screening
 
MRI sequences:
 
 • High-resolution T1 weighted • T2* weighted sequence (task-based) during task practice • Physiological recordings 	Center for Biomedical Imaging	2 – 2.5 hours

D3. DATA ANALYSIS

D3.1 Sample Size Justification.

Given the scarcity of pilot data on stroke and control participants and fMRI-based dynamic connectivity during motor learning, justification has to be based on our best estimates and regarded with some caution. One of the primary goals of this project is to determine effect sizes for the follow-up grant proposal. For changes to latent connectivity characteristics induced by implicit motor learning (pre/post evaluation), empirically obtained effect size estimates were derived from the average effect size of published studies involving participants with chronic stroke⁹ and healthy volunteers⁵⁰. Consequently, sample sizes of 25 and 15 in the stroke survivors and healthy volunteers will allow us to estimate the for the main effect of time (pre/post learning) the within-group effect sizes can be expected to be in the range of 0.33 - 0.52 at 90% confidence level.

D3.2 Analysis Plan.

Imaging Preprocessing. Data will be processed by the CBI Computational Core led by [name]. Preprocessing parameters for the task-based fMRI data will be optimized to fit the requirements of the representational similarity analysis (RSA, described below), specifically smoothing will be reduced to allow for better multivariate pattern detection. Resting-state fMRI data will undergo in-house standard preprocessing.

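### The 30-day reuse rule has no anchor and no condition on intervening treatment, so Aim 2 could link a pre-treatment motor score to a post-treatment scan

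*Combined protocol and SAP*

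**What the plan says.** The reuse rule stands in D1.4 Procedures, after the paragraph on additional questionnaires. It applies to people who have "participated in a study at the Stroke Recovery Research Center involving the same standardized assessments and questionnaires and consented to data sharing", and for them "we will use the already available data if these have been collected within ≤30 days". Its stated purpose is to reduce burden.

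The surrounding text that bears on it:

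- **Recruitment (D1.1).** The stroke group comes from a registry of "participants consented for future contact to support stroke recovery research conducted at MUSC", so recent participation in other recovery studies is to be expected.
- **Eligibility (D1.2, D1.3).** No criterion concerns rehabilitation, brain stimulation or a concurrent or recent interventional study. The stroke-specific items closest to treatment are "uncontrolled hypertension despite treatment; intake of tricyclic anti-depressants or neuroleptic medication".
- **What is measured when.** In session 2, "participants of the stroke group undergo the assessment of their upper-extremity sensorimotor functioning"; the battery is UEFMA, ARAT, 9HPT and dynamometer testing. The session 4 entry in D2 Timeline is "T2* weighted sequence (task-based) during task practice". No maximum interval between sessions 2 and 4 is given.
- **Aim 2.** The plan promises that "we will comprehensively describe upper-extremity sensorimotor functioning and impairment for the individuals in the SG" and that it will "statistically integrate these biomarkers of recovery with the ML-related network dynamics within a separate representational model".
- **Analysis (D3.2, D3.3).** No variable marks reused data, the interval to the scan or intervening treatment. The covariates named in D3.3 are sex, age, race and ethnicity.

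**The concern.** Aim 2 is informative only if the motor score and the network measure describe the same state of the same person. As written, the rule allows this sequence: a participant has UEFMA and ARAT taken as the baseline of another study at the center, receives that study's intervention, enters this study with those scores carried over, and is scanned in session 4. No rule in the plan is broken.

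The study's own rationale makes this relevant. Section B starts from experience-dependent plasticity, and the introduction describes motor-network reorganization that reflects restored function. An intervention between score and scan could therefore change either side of the pairing.

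The missing anchor adds to the problem. If the 30 days run back from consent or from session 2, a reused score may be more than 30 days old at the scan. If neither reuse nor exposure is recorded, the affected participants cannot be identified later. That matters in a pilot whose purpose is to supply effect sizes for a follow-up application.

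**Working it through.** The plan states no figure on this point, so there is nothing to reproduce. The check has two parts.

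**1. Does any passage prevent the mismatch?**

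| Where a safeguard could stand | What is there |
|---|---|
| Reuse rule, D1.4 | Age limit and data-sharing consent; no anchor, no limit to observational studies, no re-test after an intervention |
| Eligibility, D1.2 and D1.3 | Two drug classes and uncontrolled hypertension; nothing on rehabilitation, stimulation or other trials |
| Timeline, D2 | Order of sessions; no maximum gap from session 2 to session 4 |
| Analysis, D3.2 and D3.3 | No reuse, interval or treatment variable |
| Appendix 2 | Title covers demographics, education and medication; items not shown |

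No visible passage closes the gap.

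**2. How large could the effect on Aim 2 be?** The inputs below are assumptions, because the documents give none. The recorded score is taken as the current score minus a treatment shift. The shift occurs in a share f of the stroke group and has mean m and SD s, in SD units of the score. It is taken as unrelated to the current score and to the network measure. Here f counts only people who have a reused score **and** were treated between that score and the scan.

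- Variance of the recorded score: 1 + f(1 − f)m² + f·s²
- Multiplier on the correlation: 1 / √(1 + f(1 − f)m² + f·s²)

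| f | m | s | Variance | Multiplier | A true r of 0.50 becomes |
|---|---|---|---|---|---|
| 0.1 | 0.25 | 0.25 | 1 + 0.0056 + 0.0063 = 1.012 | 0.994 | 0.497 |
| 0.2 | 0.5 | 0.5 | 1 + 0.04 + 0.05 = 1.09 | 0.958 | 0.479 |
| 0.4 | 0.5 | 0.5 | 1 + 0.06 + 0.10 = 1.16 | 0.928 | 0.464 |
| 0.5 | 1 | 1 | 1 + 0.25 + 0.50 = 1.75 | 0.756 | 0.378 |

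With N = 25, f = 0.2 means 0.2 × 25 = 5 participants, and f = 0.5 means 12.5.

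For scale, the 95% interval for r = 0.50 at N = 25 by Fisher's z is 0.549 ± 1.96/√22 = 0.549 ± 0.418, or 0.131 to 0.967. Back-transformed, this is 0.13 to 0.75. Even the most extreme row (0.378) lies inside it.

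If the response to treatment is related to the network measure, the covariance between score and network changes as well. The bias can then go in either direction, and the multiplier above no longer applies.

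**The case against.** The strongest reply is that the harm is only a possibility. It needs a chain: reused data, from an interventional study, assessed before treatment, then treated, then scanned here. No document says that any step occurs. This stands, and it limits the size of the point. It does not remove the gap, because the rule itself foresees recent participation in other studies and sets no condition on it.

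Other replies also stand in part. The resting-state biomarkers in D3.2 come from this study's own scans and are untouched, so only the clinical and behavioral scores are exposed. D3.2 averages matrices within group and does not spell out the Aim 2 model, so a person-level correlation is a reading of the aim. Freshly collected session 2 data also have no maximum gap to the scan. The items in Appendix 2 are not shown, so it may already ask about therapy.

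Several stronger readings are tempting and are not supported:

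- **That the rule biases Aim 1.** Reusing a clinical score does not alter the scans. Recent treatment in the stroke group could affect the group comparison, but it would do so with or without reuse.
- **That the 0.33 to 0.52 range in D3.1 is a yardstick.** Those are within-group effects of time (pre/post learning), so a between-group or biomarker shift cannot be expressed as a share of them.
- **That everyone recently treated is mismatched.** A treated participant who is tested afresh in session 2, after the treatment, is not.
- **That the plan requires chronic stroke so that function is stable.** D1.1 gives a narrower reason, the spontaneous recovery of cognition.
- **That task force is scaled to an outdated MVC.** Dynamometer testing is listed for the stroke group only, yet controls do the same task scaled to MVC for each hand. This suggests a separate calibration, although the text does not settle it.

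**Conclusion.** The point holds as a gap in the reuse rule that affects Aim 2. Followed as written, the rule can join a motor score from before an intervention to task networks from after it, and nothing in the visible plan detects or prevents this.

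The size is unknown and probably small. Over the assumed range, the Aim 2 correlation is multiplied by 0.99 to 0.76, with 0.96 in the mid case, and sampling error at N = 25 is much larger. The loss becomes material only if reuse across a treatment is common and responses vary widely. These figures rest on assumed shares and shifts, on person-level pairing, and on a shift unrelated to both the current score and the network measure.

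This is a cheap improvement to a pilot, not a threat to its validity.

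**What to change.** 1. State the session from which the 30 days count back, for example the session 4 scan.
2. Reuse motor assessments only if no study intervention was delivered between that assessment and session 4. Otherwise repeat the battery already scheduled for session 2.
3. Record for every participant whether data were reused, the interval from assessment to session 4, and any recent exposure to an interventional study or arm-therapy program. Recording the interval for everyone also covers freshly collected scores, which have no stated limit.
4. Repeat the Aim 2 analysis without the affected participants and report both results.
5. State that the MVC used to scale task force is measured for this study.

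The cost is a few lines of protocol text, a small addition to data collection and one sensitivity analysis. The downside is that a few participants lose the burden saving and complete a battery that session 2 already includes.
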